7.5 SECONDARY ENDPOINT(S)

7.5.1 Key secondary endpoint(s)

This section is not applicable as no key secondary endpoint has been specified.

7.5.2 (Other) Secondary endpoint(s)

For each of the secondary endpoint described below, hybrid strategy will be used to handle intercurrent events which lead to data censoring as described for the primary endpoint.

Continuous secondary endpoints

The continuous secondary endpoints up to Week 12 will be analysed using a MMRM approach based upon the model specification as described for the primary endpoint.

Additionally, subgroup analysis will be performed for variables as described in [Section 6.4](#).

Binary secondary endpoints

The binary secondary endpoints will be evaluated descriptively by treatment arm via frequency tables (with 95% confidence interval based on the Wilson score for each group and based on the Chan and Zhang method for risk difference). As in the case of the primary estimand, any binary data collected after use of any rescue therapy will be censored and then imputed using the NRI method as described in CTP section 7.3 “Handling of Missing Data”.

Example SAS code for CI of proportion difference by Chan and Zhang method is as follows:

```
PROC FREQ DATA=data;  
<WHERE treat IN ('Treatment_1','Treatment_2') ;>  
TABLES treat*endpoint_bin / RELRISK RISKDIFF.  
EXACT RELRISK (METHOD=SCORE column=2) RISKDIFF (METHOD=SCORE  
column=2);  
RUN;
```

For selected binary endpoint, e.g., achievement of HiSCR at Week 12, following additional analyses are planned.

Logistic regression analysis

Proprietary confidential information © 2021 Boehringer Ingelheim International GmbH or one or more of its affiliated companies
The difference in the proportion of patients with a response between Spesolimab and placebo will be analysed using predictive margins in a binary logistic model via %Margins in SAS®. Fixed classification effects will include treatment and stratification factor (TNFi-naive population versus TNFi-failure population).

Example SAS code:

```
%Margins(data= data,  
class    = treat stratum,  
response = endpoint_bin,  
roptions = event='1',  
dist     = binomial,  
model    = treat stratum,  
margins  = treat,  
options  = cl diff)
```

Stratified risk difference

[figure not shown]
A Mantel-Haenszel type weighted average of differences will be implemented with corresponding Wald confidence intervals based on the variance formula provided by Sato.

[figure not shown]
Example SAS code:

[figure not shown]
```
Proc freq data=data;  
tables stratum*treat*endpoint_bin/cmh commonriskdiff(cl=mh);  
quit;
```

In addition, sensitivity analyses utilizing MAP Bayesian method for achievement of HiSCR at Week 12, will be considered. For the process, please refer to [section 7.4.2](#) as described for the primary endpoint. The MAP prior derivations for placebo arm obtained from Humira Pioneer I and Pioneer II trials, as well as posterior distribution for the treatment difference will be implemented following [Section 10.3.2](#).

Please refer to [Section 7.8.1](#) for the analysis of safety endpoint as a secondary endpoint, which is defined as the occurrence of Treatment Emergent Adverse Events (TEAEs).

7.7 EXTENT OF EXPOSURE

An overall table will be summarized for the entire maintenance treatment period. The number of subjects who received a dose of trial drug will be tabulated. Treatment exposure will be assessed as the total dose of randomized treatment [mg] administered for the loading stage, the maintenance stage, as well as the overall dose across the two stages, which will be summarised by descriptive statistics (N, mean, SD, minimum, median, maximum). The total duration of exposure [days] will also be displayed.

7.8 SAFETY ANALYSIS

All safety analyses will be performed on the safety analysis set.

All safety analyses will be performed following BI standards. No hypothesis testing is planned. OC-IR and OR methods will be used for safety reporting. All safety analysis will be performed for on-treatment period.

AE and possibly clinically significant laboratory abnormalities will be analyzed under OR (as defined in [Section 6.6.3](#)); the safety data by visit, i.e., laboratory, vital signs and local tolerability, will be analysed under OC-IR (as defined in [Section 6.6.3](#)).

As the onset time of an AE will not be collected in the trial, any AE which occurs on the same day as a treatment dose will be assigned to the “post treatment”. For safety assessments by visits, if time is not collected, data on the same day of a treatment dose will be treated to be “prior treatment” except for scheduled local tolerability and post-dose vital signs assessments.

Off-treatment data will be listed only.

Additional analyses on AE will be also included:

AE within loading stage

Proprietary confidential information © 2021 Boehringer Ingelheim International GmbH or one or more of its affiliated companies
For AE, the additional safety tables for loading dose stage will be produced by grouping patients based on their loading doses (1200 mg, Placebo) using SAF. The outputs will include on-treatment data up to the first maintenance dose at or post week 4. If patients discontinued from treatment prior to receiving first maintenance dose, then the safety data up to the date of last loading dose + 112 days will be included.

7.8.1 Adverse Events

AEs will be coded with the most recent version of MedDRA.

The analyses of AEs will be descriptive in nature. All analyses of AEs will be based on the number of patients with AEs and not on the number of AEs. System organ classes (if applicable) will be sorted according to the standard sort order specified by the EMA, preferred terms (if applicable) will be sorted by total frequency (within system organ class).

For details on summarization of AE data, please refer to "Handling and summarization of adverse event data for clinical trial reports and integrated summaries" (15) and "Handling of missing and incomplete AE dates" (4).

The analysis of AEs will be based on the concept of treatment-emergent AEs. This means that all AEs will be assigned to the screening period, loading treatment phase, maintenance period (i.e. maintenance treatment phase plus REP) or off-treatment period (i.e. follow up) as defined in Section 6.1. Since only the start date of an AE is collected (without start time), any AE occurrence on the same day as the first Spesolimab administration will be assigned to the on-treatment phase.

An overall summary of AEs will be presented by treatment. This overall summary will include summary statistics for the class of other significant AEs (sponsor definition based on ICH E3) and for the class of AESIs.

The following is considered an AESI in this trial:

Systemic hypersensitivity including infusion reaction and anaphylactic reaction

Severe infections (according to RCTC grading)

Opportunistic and mycobacterium tuberculosis infections

Hepatic injury

A hepatic injury is defined by the following alterations of hepatic laboratory parameters:

- an elevation of AST (Aspartate Aminotransferase) and/or ALT (Alanine Aminotransferase) ≥ 3 fold ULN combined with an elevation of total bilirubin ≥ 2 fold ULN measured in the same blood draw sample, or in samples drawn within 30 days of each other
OR
- aminotransferase (ALT, and/or AST) elevations ≥ 10 fold ULN.

Proprietary confidential information © 2021 Boehringer Ingelheim International GmbH or one or more of its affiliated companies
 In addition, user defined adverse event concepts (UDAEC) identified through specific search criteria will be reported separately (see [Table 7.8.1:1](#)).

Table 7.8.1: 1 Project MEDDRA search criteria for User Defined Adverse Events Concepts

User-defined AE category		
	Label	Description
Hypersensitivity	Hypersensitivity ALL	Combined search strategy based on the three individual UDAECs described below
	Anaphylactic reaction, narrow	Narrow SMQ “Anaphylactic reaction”
	Angioedema, narrow	Narrow SMQ “Angioedema”
	Hypersensitivity, narrow	Narrow SMQ “Hypersensitivity”
Infections (serious/severe, opportunistic)	Infections 'ALL'	terms from combined search with sort order # in (20, 30, 40, 21, 22) Sort order if applicable to project or trial
	Opportunistic infections	SMQ "Opportunistic infections", narrow
	Tuberculosis infections	sub-BIcMQ “Tuberculosis related terms”, narrow BIcMQ "Infections", sub-search 8.2 “Tuberculosis related terms” narrow
	Severe infections	SOC "Infections and infestations" with AETOXGR >= 3 OR AESEV = 'Severe'. Not derived for studies where both severity variables are collected. SOC "Infections and infestations" of at least severe RCTC grade (>= 3) or any severe events
	Serious infections	SOC “Infections and infestations” with [AECOND: AESER = 1] SOC “Infections and infestations” with "intensity= serious"
Malignancies	Malignant tumours	sub-SMQ “Haematological malignant tumours”, narrow, sub-SMQ “Non-Haematological malignant tumours”, narrow
	Malignancies excluding NMSC	sub-SMQ “Malignant tumours” excluding terms from search with sort order #=340 Sub-SMQ “Malignant tumours” excluding NMSC, where NMSC is defined above
Torsades de Pointes	Torsades de Pointes	Broad sub-SMQ “Torsade de pointes/QT prolongation”

Proprietary confidential information © 2021 Boehringer Ingelheim International GmbH or one or more of its affiliated companies

Depression	Depression	sub-SMQ "Depression (excl suicide and self-injury)", broad
Suicidal ideation and behavior (SIB)	sub-SMQ "Suicide/self-injury"	
DRESS	DRESS (Drug reaction with eosinophilia and systemic symptoms syndrome), broad	SMQ "Drug reaction with eosinophilia and systemic symptoms syndrome", broad Algorithm: A or (B and C and D) or (B and C and E) or (B and D and E)
	DRESS (Drug reaction with eosinophilia and systemic symptoms syndrome), narrow	SMQ "Drug reaction with eosinophilia and systemic symptoms syndrome", narrow Only category A

* this is achieved by retrieving all cases found either by running subsearch 1 in narrow scope (BICMQ search ID 32019093) or subsearch 2 (BICMQ search ID 32019094)

The frequency of patients with AEs will be summarised by treatment, primary system organ class and preferred term. AEs which were considered by the investigator to be drug related will be summarised separately. Separate tables will also be provided for patients with SAEs, patients with AESIs, patients with AE leading to discontinuation of the trial medication, and patients with other significant AEs (as described previously). AEs will also be summarized by maximum intensity.

For disclosure of AE data on ClinicalTrials.gov, the frequency of patients with non-serious AEs occurring with an incidence of greater than 5 % (in preferred terms) will be summarised by treatment, primary system organ class and preferred term. The frequency of patients with SAEs and drug related SAEs will also be summarised respectively.

For disclosure of AE data in the EudraCT register, the frequency of non-serious AEs with an incidence of greater than 5 % (in preferred terms) and the frequency of SAEs will be summarised.

7.8.2 Laboratory data

The analyses of laboratory data will be descriptive in nature and will be based on BI standards (16). Note that data from the central Laboratory will be used for all displays described below, unless otherwise specified.

For continuous safety laboratory parameters, normalized values will be derived.

Normalisation means transformation to a standard unit and to a standard reference range. The process of normalisation, handling of repeat values at the same visit for by-visit displays, as well as standard analyses for safety laboratory data are described in the BI guidance for the Display and Analysis of Laboratory Data (16). All analyses considering multiple times of the ULN (as described below) will be based on standardized and not normalized values. For continuous safety laboratory parameters, differences to baseline will be calculated. For all outputs, the last assessment before the first treatment at Day 1 is chosen as the baseline value.

Proprietary confidential information © 2021 Boehringer Ingelheim International GmbH or one or more of its affiliated companies
Only patients with at least one available post-baseline value will be included in the analysis of an individual laboratory parameter. All individual laboratory data will be listed. Values outside the reference range will be flagged.

For derivation of the last value, the minimum value, and the maximum value, all values during the entire treatment period will be considered under OR. These will be derived for analysis of laboratory, vital signs and local tolerability data. For identification of potentially clinically significant abnormal laboratory values, all values during entire treatment period will also be considered under OR.

Descriptive statistics of laboratory values over time and for the difference from baseline on-treatment (see [Section 6.7](#)) will be based upon normalized values and provided by visit (including follow up) under OC-IR, including summaries of the last value on treatment, the minimum value on treatment and the maximum value on treatment. Graphical displays via box plots will be produced for the change from baseline, over time, for each continuous laboratory endpoint.

Laboratory values will be compared to their reference ranges; shift tables will be provided for the number of patients with a specific RCTC grade at baseline versus the grade at the last measurement on treatment, as well as the worst grade on treatment. These analyses will be based on standardized laboratory values.

Potentially clinically significant abnormalities will be identified based on BI standard rules which are based on converted lab values, i.e. using SI units. These rules will be listed in the SDL appendix of the CTR. Frequency tables will summarize the number of patients with potentially clinically significant abnormalities. Patients having an abnormal lab value at baseline will be presented separately. A separate listing will present potentially clinically significant abnormal lab values; for each functional lab group all patient's lab values will be listed, if there exists at least one lab value with clinically significant abnormality within the group.

The frequency of patients with AST or ALT elevations $\geq 3xULN$, $\geq 5xULN$, $\geq 10xULN$, and $\geq 20xULN$ will be displayed based on standardized laboratory values. To support analyses of liver related adverse drug effects, the frequency of patients with AST and/or ALT $\geq 3xULN$ combined with a total bilirubin $\geq 2xULN$ in a 30 day period after AST/ALT elevation will be displayed, stratified by alkaline phosphatase $< 2xULN$ and $\geq 2xULN$ (a patient can potentially be in both alkaline phosphatase strata in case of multiple AST/ALT and bilirubin elevations). The start of the 30 day time span is triggered by each liver enzyme elevation above the defined thresholds. This analysis will be based on standardized laboratory values.

A graphical analysis of the ALT, AST and total bilirubin during the on-treatment period will also be performed; the so called eDISH plot. In the graph, for each subject, the peak total bilirubin is presented as a fold increase over the ULN against the peak ALT as a fold increase over the ULN, on a log₁₀ scale. The measurements displayed of total bilirubin and ALT may, or may not, occur on the same date. Two reference lines, 2xULN for total bilirubin and 3xULN for ALT, are drawn onto the graph in order to divide the plane into four quadrants. Normal cases are in the lower left quadrant, potential DILI cases are in the upper right quadrant (Hy's Law quadrant), while the lower right quadrant is known as the Temple's corollary range (ALT $\geq 3xULN$ and total bilirubin $< 2xULN$).

Proprietary confidential information © 2021 Boehringer Ingelheim International GmbH or one or more of its affiliated companies
Clinically relevant findings in laboratory data will be reported as baseline conditions (at screening) or as AEs (during the trial) if judged clinically relevant by the investigator, and will be analyzed as such.

7.8.3 Vital signs

The analyses of vital signs (blood pressure, pulse rate, body temperature, respiratory rate) and body weight will be descriptive in nature. Descriptive statistics of vital signs over time and for the difference from baseline (see [Section 6.7](#)) will be provided, including the last value, the minimum value and the maximum value during on-treatment period.

Clinically relevant findings in vital signs data will be reported as baseline conditions (at screening) or as AEs (during the trial) if judged clinically relevant by the investigator, and will be analysed as such.

7.8.4 ECG

Abnormal findings in 12-lead ECG will be reported as baseline conditions (at screening) or as AEs (during the trial) if judged clinically relevant by the investigator, and will be analysed as such.

No separate listing or analysis of ECG data will be prepared.

7.8.5 Local tolerability

Local tolerability will be summarized by visit under OC-IR, with the frequency and percentage of patients who experienced any symptoms by severity/intensity.

7.8.6 Others

Not applicable.

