Visit	1	2 Baseline	3	4	5	6	7	8	EoT ²	FUP 1	EoS	
Day	-28 to -1	1 ¹	8	15	29	43	57	71	85	56 days after last drug admin.	112 days after last drug admin.	
Weeks	-4	0	1	2	4	6	8	10	12	8 weeks after last drug admin.	16 weeks after last drug admin.	
Time window for visits (days)	n.a.	none	±1	±1	±3	±3	±3	±3	±3	±7	+7	
Abscess count	X	X	X	X	X	X	X	X	X			
Inflammatory nodule count.												
Non-inflammatory nodule count												
Draining Fistula count.												
Photography		X			X				X			
Hidradenitis Suppurativa Clinical Response (HiSCR)			X	X	X	X	X	X	X			
International Hidradenitis Suppurativa Severity Score System (IHS4)	X	X	X	X	X	X	X	X	X			
Hidradenitis Suppurativa Area Severity Index (HASI)		X	X	X	X	X	X	X	X			
Hidradenitis Suppurativa Physician's Global Assessment (HS-PGA)	X	X	X	X	X	X	X	X	X			
Dermatology Life Quality Index (DLQI)		X	X		X		X		X			
Hidradenitis Suppurativa Quality of Life (HiS-QoL)		X	X		X		X		X			
FACIT-Fatigue scale		X	X		X		X		X			
Patient Global Assessment of Change (PGI-C)			X		X		X		X			
Patient Global Assessment of Severity (PGI-S)		X	X		X		X		X			
Columbia-Suicide Severity rating Scale (C-SSRS) ¹²	X	X	X	X	X	X	X	X	X	X	X	

Trial Periods	Screening	Treatment Period								EoT	Safety Follow-Up	
Visit	1	2 Baseline	3	4	5	6	7	8	EoT ²	FUP 1	EoS	
Day	-28 to -1	1 ¹	8	15	29	43	57	71	85	56 days after last drug admin.	112 days after last drug admin.	
Weeks	-4	0	1	2	4	6	8	10	12	8 weeks after last drug admin.	16 weeks after last drug admin.	
Time window for visits (days)	n.a.	none	±1	±1	±3	±3	±3	±3	±3	±7	+7	
Dispense Patient's Diary ¹³	X	X	X	X	X	X	X	X				
Review returned Patient's Diary ¹⁴		X	X	X	X	X	X	X	X			
All adverse events ¹⁵	X	X	X	X	X	X	X	X	X	X	X	
Concomitant therapy	X	X	X	X	X	X	X	X	X	X	X	
Roll over into OLE trial ¹⁶									X			
Completion of patient participation											X	

1 Day of Randomization / Day of first intake of randomized medication. If needed, some visit 2 assessments may be conducted 2 days before or after the actual visit date after consultation with the Sponsor.

2 Patients who discontinue trial treatment prematurely-should undergo the End of Treatment (EoT) visit as soon as possible. All patients not entering the OLE trial are expected to complete the EoT visit, a FUP1 visit 8 weeks after their last trial drug intake and a final EoS visit 16 weeks after their last trial drug intake. For patients entering the OLE trial at week 12, the EoT visit will be their EoS visit in trial 1368-0052. (see also footnotes #8 and #16)

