Blood sampling	
As with all blood sampling, there is a risk of mild pain, local irritation, or bruising (a black or blue mark) at the puncture site.
 
Furthermore, there is a small risk of lightheadedness and/or fainting. In rare cases, the puncture site can also become infected or nerves may be damaged, inducing long-lasting abnormal sensations (paresthesia), impaired sensation of touch and persistent pain.
	
These risks will be addressed by careful safety monitoring and risk mitigation measures such as
 
 (a) close clinical monitoring for AEs; (b) selection of experienced sites and site staff; (c) Safety recommendations provided in laboratory manual.
Skin biopsy	
Can cause local bruising, inflammation, nerve damage and pain.
	
These risks will be addressed by careful safety monitoring and risk mitigation measures such as
 
 (a) close clinical monitoring for AEs; (b) selection of experienced sites and site staff; (c) staff training
Other risks		

Administration of Placebo	If the patient is randomized to receive a placebo, the patient's condition could get worse during the trial.	Minimize the number of patients on the placebo group using adequate statistical model. The use of rescue medication is foreseen in this trial for patients experiencing a worsening of their HS condition.
Suicidal ideation and behavior	Increased risk of suicidal ideation and behavior is present in the population of patients with hidradenitis suppurativa	'Baseline/ screening' version of C-SSRS will be administered with the aim to exclude patients with active moderate to severe symptomatology present within a specified time prior to the screening or screening visit. 'Since last visit' version of C-SSRS will be administered with the aim to monitor patient's safety during the trial and to initiate actions for the patient's safety if such actions are deemed necessary. All C-SSRS reports of suicidal ideation type 4 or 5 and all reports of suicidal behavior represent SAEs and are subject to close monitoring.

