5.2.5.1 Suicidality

Suicidal thoughts and behavior will be assessed by the Columbia-Suicide Severity Rating Scale (C-SSRS, [\[R08-1147\]](#)).

The C-SSRS is a semi-structured, investigator-rated interview, developed by clinical experts in cooperation with the FDA, assessing both suicidal behavior and suicidal ideation. It does not give a global score, but provides some categorical and some severity information specifically for behavior and ideation.

The C-SSRS interview may be administered by any type of physician, psychologist, clinical social worker, mental health counselor, nurse, or coordinator with C-SSRS training. It has a typical duration of five minutes, and causes only a low burden on subjects. At a minimum, the interview consists of 2 screening questions related to suicidal ideation and 4 related to suicidal behavior, and may be expanded to up to 17 items in case of positive responses. Free text entries are allowed for; the investigator has to directly evaluate the scale and write a report. In this trial paper forms will be used for the assessment of the C-SSRS® and results will be transcribed into the e-CRF.

The C-SSRS has been widely used in large multinational clinical trials. The C-SSRS will be administered at the Screening Visit/Visit 1 (using the 'baseline/ screening' version) with the aim to exclude patients with active moderate to severe symptomatology within a specified time prior to the screening or screening visit. The lifetime and the past year history of suicidal ideation and behavior will also be recorded.

After the screening visit, the assessment 'since last visit' version will be performed at each visit. The investigator is to review positive and negative reports for plausibility and clinical relevance. Doubtful reports may be repeated or reports may be validated by a consulting

psychiatrist or other mental health professional expert. If there is a confirmed positive report of suicidal behavior or suicidal ideation type 4 or 5 after start of trial, the investigator is to immediately interview the patient, and/or is to consult a mental health professional. If the positive report is confirmed, appropriate actions for the patient's safety have to be initiated. All C-SSRS reports of suicidal ideation type 4 or 5 and all reports of suicidal behavior must be reported as separate SAEs by the investigator.

For 'Self-injurious behavior, without suicidal intent', standard AE / SAE reporting rules are to be applied.

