For each negative report (suicidal ideation type 1, 2 or 3) after the start of the trial, the investigator is to decide based on clinical judgment whether it represents an Adverse Event (AE) as defined in the protocol, and if it is considered an AE then it must be reported accordingly.

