7.2.5 Safety analyses

Adverse events will be coded using the current version of Medical Dictionary for Regulatory Activities (MedDRA) coding dictionary. Standard Boehringer Ingelheim's summary tables and listings will be produced.

All randomized and treated patients will be included in the safety analysis. In general, safety analyses will be descriptive in nature and will be based on BI standards. No hypothesis testing is planned. Statistical analysis and reporting of adverse events will concentrate on treatment-emergent adverse events (TEAE). To this end, all adverse events occurring between start of treatment and end of the residual effect period will be considered 'treatment-emergent'; the residual effect period (REP) is defined as 16 weeks after the last dose of trial medication. Adverse events that start before first drug intake and deteriorate under treatment will also be considered as 'treatment-emergent'.

Frequency, severity, and causal relationship of adverse events will be tabulated by system organ class (SOC) and preferred term after coding according to the current version of the MedDRA at database lock.

Laboratory data will be analysed both quantitatively as well as qualitatively. The later will be done via comparison of laboratory data to their reference ranges. Values outside the reference range as well as values defined as clinically relevant will be highlighted in the listings. Treatment groups will be compared descriptively with regard to distribution parameters as well as with regard to frequency and percentage of patients with abnormal values or clinically relevant abnormal values. Vital signs, physical examinations, or other safety-relevant data observed at screening, baseline, during the course of the trial and at the end-of-trial evaluation will be assessed with regard to possible changes compared to findings before start of treatment.

Immunogenicity data will be analysed in a descriptive way.

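### SAP 7.8 plans no C-SSRS summary, so emergent type 1–3 ideation that is not reported as an adverse event is at most listed, with no comparison by arm and no change from pre-treatment status

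*SAP*

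**What the plan says.** Protocol Table 1.4.2:1, under its other-risks heading, states: "Increased risk of suicidal ideation and behavior is present in the population of patients with hidradenitis suppurativa". The Flowchart marks the C-SSRS in every column: screening, Visits 2 to 8, EoT, FUP1 and EoS. Protocol 5.2.5.1, which sits under 5.2.5 (Other safety parameters), says that after screening the since-last-visit "version will be performed at each visit", and that "results will be transcribed into the e-CRF". Lifetime and past-year history are also recorded at screening.

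The same section sets the route into adverse event data. Ideation of type 4 or 5 and all suicidal behaviour "must be reported as separate SAEs by the investigator". "For each negative report (suicidal ideation type 1, 2 or 3) after the start of the trial", the investigator decides on clinical judgement whether it is an AE, and reports it if so.

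Protocol 7.2.5 says that "Vital signs, physical examinations, or other safety-relevant data observed at screening, baseline, during the course of the trial" and at its end will be assessed for possible change from findings before treatment.

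The SAP introduction says that the plan specifies the trial's analyses in full. SAP 7.8 names laboratory data, vital signs and local tolerability as the by-visit safety data. Its subsections cover AEs (7.8.1), laboratory (7.8.2), vital signs (7.8.3), ECG (7.8.4) and local tolerability (7.8.5). Section 7.8.6 (Others) reads "Not applicable". SAP Table 7.8.1:1 includes an AE category for suicidal ideation and behaviour (SIB), found by a standard MedDRA query and reported separately.

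**The concern.** The protocol treats the C-SSRS as a safety parameter, collects it at every visit for a named risk, and records a pre-treatment reference for it. An analyst who follows SAP 7.8 would produce no output from it. What the report could say by arm about suicidality would depend on what was recorded as an AE.

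For the most serious categories that is no loss, because reporting is mandatory. For types 1–3 (wish to be dead, non-specific active thoughts, thoughts with a method but no intent) it depends on a case-by-case decision. New type 1–3 ideation could differ between arms without any planned table showing it. Worsening from pre-treatment status, which is the kind of assessment that Protocol 7.2.5 describes, would not be shown for any category.

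**Working it through.** The plan gives no figure to reproduce. The check traces each kind of C-SSRS report from Protocol 5.2.5.1 to the outputs in SAP 7.8.

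| C-SSRS report after treatment start | Route into AE data | Planned by-arm output in SAP 7.8 |
|---|---|---|
| Ideation type 4 or 5 | Mandatory SAE | AE and SAE tables; SIB if the coded term is in the query |
| Suicidal behaviour | Mandatory SAE | As above |
| Self-injury without suicidal intent | Usual AE/SAE rules | AE tables if reported |
| Ideation type 1–3, judged an AE | AE | AE tables; SIB if the coded term is in the query |
| Ideation type 1–3, not judged an AE | None | None |
| Change from pre-treatment, any category | None | None |

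**What the two empty rows still get.** SAP 7 (General Remarks) says that individual values of all patients will be listed. A listing sorted by country, centre and patient is not a summary by arm.

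**Whether the omission is recorded as a choice.** For ECG, SAP 7.8.4 routes clinically relevant findings through AEs and says that there will be no separate listing or analysis. No such statement is made for the C-SSRS. In the readable SAP the instrument is named only in protocol-deviation code A2.17, an eligibility criterion.

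**Counts.**
- C-SSRS scheduled: 11 of 11 Flowchart columns. Subsections of SAP 7.8 that plan a summary of it: 0 of 6.
- Ideation types outside mandatory SAE reporting: 3 of 5.
- Assessments after baseline to Week 12: 7 per patient (Weeks 1, 2, 4, 6, 8, 10, 12). For 45 patients, 7 × 45 = 315 at most. This is the volume of data collected, not the number of reports missed.
- Weight of one patient: 1/30 = 3.3% on spesolimab, 1/15 = 6.7% on placebo.

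**Which look-back a shift table needs.** Protocol 3.3.3 excludes type 4 or 5 ideation in the past 12 months. With a past-year look-back, eligible patients therefore enter from screening with no ideation or types 1–3, which leaves room to see worsening. With a lifetime look-back, a patient with lifetime type 3 could never count as emergent for new type 1–3 ideation.

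**The case against.** A reader might infer that type 1–3 ideation is never compared by arm, or that none of the 315 assessments is summarised. The documents do not support either. A type 1–3 report judged to be an AE must be reported; it is then tabulated by treatment and may fall in the SIB category. Types 4–5 and behaviour reach the SAE tables. Individual values are listed, and an external DMC sees unblinded safety data.

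A reader might also say that the instrument exists to avoid reliance on AE judgement. The protocol does not say that. Table 1.4.2:1 gives its purposes as exclusion at screening, then monitoring and action for patient safety, and 5.2.5.1 calls it investigator-rated. Nor does Protocol 7.2.5 promise a C-SSRS shift table: it names neither the instrument nor a format. The bulleted list in Protocol 5.2 of what the descriptive safety assessment rests on omits the C-SSRS, and the risk is described as one present in the HS population, not as a spesolimab risk.

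All of this stands and narrows the point without removing it. The SIB category retrieves only events already recorded as AEs. Listings and DMC outputs (under a separate DMC SAP) are not a planned by-arm report. Section 5.2.5.1 lies within Protocol 5.2, and the wording of 7.2.5 is not confined to the bulleted list. Routing a measure through AEs alone can be a legitimate choice, but the SAP states that choice for ECG and not here.

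Parts of the SAP, including 7.6 and the appendices, are not in the released text, so a C-SSRS display there cannot be excluded.

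**Conclusion.** The gap is real but limited. SAP 7.8 plans no C-SSRS summary. Suicidality is tabulated by arm only through AEs and SAEs, including SIB. Emergent type 1–3 ideation that the investigator does not report as an AE is at most listed, and no change from pre-treatment status is shown.

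The size cannot be put as a number of missed reports: the documents give neither a rate of type 1–3 ideation nor the share that would be reported as AEs. The conclusion assumes that no C-SSRS display sits in the unreleased SAP sections; the statement about 7.8 itself does not depend on that, because 7.8.1 to 7.8.6 can all be read.

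No primary or secondary efficacy result is affected, and the most serious categories are already captured. The plan should still be changed, because a risk that the protocol names lacks a readout from the instrument collected for it, and the remedy is cheap.

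**What to change.** Replace the entry in SAP 7.8.6 with two descriptive displays on the SAF, for the on-treatment period as defined in SAP Table 6.1:1:

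1. By arm, the number and percentage of patients by worst ideation type (1 to 5), with any suicidal behaviour, and with self-injury without suicidal intent.
2. A by-arm shift table from worst pre-treatment to worst on-treatment category. Fix the pre-treatment look-back as the past-year history at screening plus any pre-dose Visit 2 report. Show lifetime history separately so that it does not mask new ideation.

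If the sponsor prefers AE reporting alone, the SAP should say so, as it does for ECG. If a display already exists in an unreleased section, a cross-reference in 7.8.6 is enough.

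The cost is one SAP paragraph and two tables from eCRF data already collected. No visit, stopping rule or clinical management changes. The tables will be sparse with 30 and 15 patients, so they should be read as counts.
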